Official Title of the study: Utilizing Digital Health Approaches to Promote Early Childhood Healthy Eating and Activity Behaviors

NCT number (if available): Pending

Date of the document: January 6, 2025

eHEROs (Know How) Pilot Study Overview

The overall aim of the electronic HEalthy EnviROnments study (eHEROs) is to transform a tested, traditional, in-person parent intervention for families of young children to a digital platform promoting healthy eating and activity behaviors and environments, and ultimately healthy growth. The intervention program is called Know-How: Building Healthy Eaters and Movers (Know-How). The intervention will be 10 weeks. Week 0 will be an introduction to the overall study followed by 9 weeks of Know How programming. *Please note that the formal name of the study is e-HEROs, but participants will only see the term Know How program/study use.*

Intervention Design

The Know-How program provides parent education on the topics of mindful parenting, healthy eating, and physical literacy and will consist of 3 components: 1) a custom mobile application (app) ; 2) virtual group discussions and 3) child-centered support materials mailed to participating families.

1. Know-How app

The Know-How app will provide parent education using a variety of modalities. The ‘know’ will provide parents with the core information on mindful parenting, healthy eating, physical literacy and the ‘how’ will give strategies to incorporate the information into daily routines and activities. To facilitate the transition from the ‘know’ to ‘how’, the app will have a ‘Kid Zone’ will content to engage in activities with the preschooler. Content will be based on the theoretical constructs of the Adult Learning Theory and Social Cognitive Theory. Content will be divided into five modules that include A) lessons (text, audio, video), B) activities, and C) assessments.

A. Lessons

Table 1. Know-How Topics by Content Area	
Content Area	Topics
Mindful Parenting	
 • Parenting Mindfully • Non-Judgmental Acceptance • Listening Mindfully • Emotionally Mindful • Parenting Compassionately • Self-Regulation
Healthy Eating	
 • Offering New Foods • Mealtime Conversations • Home Food Environment
Physical Literacy	
 • Movement Skills • Active Play • Activity Opportunities
Kid Zone	
 • Intro to the Sporks Family • Let's Eat • Let's Move • Let's Go

B. Activities

To engage participants with the lesson content, activities will be interspersed within the lessons. Activities will include quizzes, goal setting and monitoring, and behavioral activities.

- *Quizzes* will inquire about participants:
 - Confidence in offering healthy foods, providing PA opportunities to child, engaging in positive interactions with child related to healthy eating, PA and modifying the home environment.
 - Knowledge on feeding and practices and misconceptions; physical literacy; and other core content.
- *Goal Setting and monitoring* activities will embed mindful parenting strategies to enactment of the 3 healthy eating topics and 3 physical literacy topics. Participants will choose at least 2 of the mindfulness prompts (watch, listen, talk, try) and plan how to practice a new behavior, record if they accomplished the plan, and reflect on the experience.
- *Behavioral activities* and reflections will provide participants with experiences to move from the ‘know’ to the ‘how’. They will be asked to choose a new food to offering their child and reflect on how it went (child’s sensory behaviors, liking, their experience and observations). Secondly, they will be asked to upload photos of meals and snack offerings to reflect on meal composition (which food groups were provided, portion sizes), environmental factors (who did the child eat with, mealtime environment/distractions) and timing and frequency of snacks. Related to physical activity, participants will upload short videos (15-30 seconds) of their child participating in a Kid Zone activity or practicing a movement skill. Parents will reflect on their interactions with the child (e.g., modeling, verbal encouragement, instruction, etc.).

C. Assessments

Two assessments will be built into the app (to complement survey distributed via REDCap) and administered at baseline and post-intervention. These assessments – Food Photography and Child Movement Skills – will require photo and video upload. To reduce participant burden of learning a new system, we have built these 2 assessments into the app.

- *Food Photography*: To assess mealtime food quality and intake, parents will be asked to take 2 photos of their child’s meal (before the child eats (pre-meal) and post-meal) on 3 days (2 weekday and 1 weekend day) over a 7-10, day period. Along with pre-meal photo, participants will be asked to provide a text description of the meal components/ingredients. Parents will have the opportunity to provide any optional text about the meal with the post-meal photo (e.g., second servings, spilled items, an additional food item added mid meal). Photos will be downloaded and stored on
- *Child Movement Skills*: To assess movement skills, parents will be asked to record their child attempting 11 movement skills in 4 groups:
 - Locomotor 1 – run, gallop slide
 - Ball skills 1 – overhand throw, underhand roll, catch
 - Locomotor 2 – hop, leap, horizontal jump
 - Ball skills 2 – dribbling and kick

2. Group Discussions

During the 9-week intervention, participants will meet via Zoom for 6, 45-60 minute sessions to connect with a trained group facilitator (member of the research team) and a group of peers (6-8)

from their cohort. The discussions will consist of 2-3 topics (e.g., picky eating, motor development) that complement the materials from the app and allow participants to discuss their experiences, successes or challenges with the material or activities. The purpose is to build community and provide social support to the participants. Embedded within the discussions will be questions about quality of conversation (Discussions 2 & 4), acceptability of program (Discussion 3) and community belongingness (Discussion 5).

3. Support materials

Materials to support both assessment (e.g., balls) and programming (e.g., chef's hat and apron, activity dots, scarves, etc.) will be mailed to participants. We anticipate ~3 mailings spread out over the program. Materials are intended to support behavioral activities and to provide incentive to engage with the children's activities (KidZone) and to continue with/complete the Know How program.

[figure not shown]
Table 2: Know How Intervention Design

Activity	Week									
	0	1	2	3	4	5	6	7	8	9
Know How App Modules	Study Overview	Introduction		Know Your Child		Know Your Self		Know Your Home		Summary
Group Discussion	1		2		3		4		5	6
Support Materials	X			X				X		

Study Design

This study is a feasibility study that will include 2 cohorts with a delayed control group (Figure 2). Study assessments will be collected at Baseline (Time 1), pre-intervention and at Post-Test (Time 2), post-intervention at the same time for both groups. No additional assessments will be collected for the delayed control group at the conclusion of implementation.

Figure 1: Study Timeline by Cohort and Intervention Group

Measures

Table 2 outlines the measures that will be collected at either Baseline (Time 1) or Post-Intervention (Time 2). Measures will be either included in the mobile app or provided to participants via REDCap.

Table 2. Feasibility Pilot Study Measures						
Activity/Testing	Measures	Variables	Data Source	Time 1	Time 2	IRB Submission
Screener	Eligibility Criteria	Inclusion: Participants must have a preschool-aged child (3-5 years) with no disabilities or conditions that impact typical eating and activity behaviors. Adult participants must have access to a smartphone, reliable internet at home, and can make video calls. Exclusion: Adults who do not have a child aged 3-5 or child has a disability/condition. Technology access is limited. Adults who read, write or speak a language other than English.	0. Screener	Prior to enrollment		✓
Participant Information	Demographics & Participant Characteristics	Demographics: Age, Gender, Race, Ethnicity, Education, Income Participant Characteristics: Digital literacy, child food fussiness, physical activity ability	1.Information Sheet	X		✓
Feasibility Primary Outcome	Recruitment	Completed interest form, eligibility status, and enrollment	Study records	X		
	Retention	Proportion of intervention and app modules completers	Study records and App backend data		X	
	Usability	Ease of use, complexity, confidence in using, likelihood of use	2. Experience with Know How Program	X		✓
	Acceptability	Ratings of information helpfulness, goal setting, liking, willingness to recommend, desire for additional information	2. Experience with Know How Program	X		✓
Implementation Outcomes Primary Outcomes	Digital Engagement	Delivery, receipt, and dosage - amount of time engaged by topic, features, and temporal patterns; completion rates of modules and within-app activities.	App backend data		X	
	Enactment	Participation in target behaviors	Data from behavioral outcomes (below); A.Focus groups and	X		✓

			B.Interviews			
	Intention to Sustain	Identify intervention strategies relating to target behaviors which were implemented or adopted	A.Focus groups and B.Interviews	X	✓	
	Peer Support	Gauge quality of conversations, sense of community as well as acceptability of programming.	3. Group Discussions	During Intervention		✓
Behavioral Outcomes Secondary Outcomes	Mindful Parenting	Listening with full attention, emotional awareness of self and child, self-regulation, compassion of self and child, non-judgmental acceptance of self and child	4. Parenting	X	X	✓
	Parenting Practices	Parent-Child Feeding Practices: Autonomy (encourages exploration of new foods, offers new foods, repeatedly presents new foods) and Structure (mealtime) Physical Activity Parenting Practices: Structure (nondirective support, supportive expectation, restriction of PA inside), Autonomy (support, guided choice) Snacking Parenting Practices: Snacks to manage behavior, snack planning, monitoring, and limit setting.	5. Child Feeding 6. Physical Activity and 7. Snacking	X	X	✓
Behavioral Outcomes Exploratory Outcomes	Home Environment	Availability of Fruit, Convenience Foods, Beverages and Whole Grains; Physical activity equipment	8. Home Health Environment	X	X	✓
	Mealtime Food Photography	Mealtime food quality & intake	9. Mealtime photos (downloaded from app)	X	X	✓
	Child Movement Skills	Locomotor skills: run, gallop, hop, leap, horizontal jump, slide Ball skills: dribbling, catch, kick, overhand throw, underhand roll	10. Movement videos (downloaded from app)	X	X	✓
	Child Dietary Intake	Frequency of child's consumption of a subset of foods – fruits, vegetables, protein, grains, beverages, dairy.	11. Child's Diet	X	X	✓
	Child Physical Activity	Opportunities for structured and unstructured PA	12. Physical Activity Opportunities	X	X	✓

Time 1= Baseline, Time 2= Post-Intervention

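### Food Photography: second servings, spills and foods added mid-meal are reported only if the parent chooses, so recorded intake is misstated when they go unreported and a blank cannot be read as none

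*Protocol*

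**What the plan says.** Under C. Assessments, the Food Photography item gives its purpose and method together: "To assess mealtime food quality and intake, parents will be asked to take 2 photos of their child’s meal", one before and one after eating, "on 3 days (2 weekday and 1 weekend day) over a 7-10, day period". The assessment is "administered at baseline and post-intervention".

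Two pieces of text go with the photos. With the pre-meal photo, "participants will be asked to provide a text description of the meal components/ingredients". With the post-meal photo the text is voluntary: "Parents will have the opportunity to provide any optional text about the meal with the post-meal photo". The examples given for the voluntary text are "e.g., second servings, spilled items, an additional food item added mid meal".

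The measures table (Table 2, Feasibility Pilot Study Measures) lists the variable as "Mealtime food quality & intake", marks it at Time 1 and Time 2, and places it among the exploratory behavioral outcomes. Study Design says that the delayed control group is assessed at the same times. Under B. Activities, the programme itself includes a similar task: "they will be asked to upload photos of meals and snack offerings to reflect on meal composition", with portion sizes among the things parents reflect on.

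**The concern.** Two photos give intake as what was on the plate before minus what is left after. That subtraction goes wrong in the three situations the Protocol lists as examples for the voluntary note. A second serving or an added item that is eaten appears in neither photo. A spilled item appears in the first and is gone from the second, so it looks eaten. The Protocol thus foresees the corrections its measure needs but does not require them.

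An empty field is then ambiguous between no event and an event not reported. This is a data-capture rule and not a matter for an analysis plan: an answer that was never asked for cannot be recovered later. At stake is the accuracy of recorded intake and, under further conditions set out below, of comparisons built on it.

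**Working it through.** The Protocol gives no figure for intake, event frequency or reporting, so there is nothing to reproduce. The numbers below illustrate the mechanism; every input is an assumption.

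**Model.** Let r be the share of events that parents write down, p_s and S the frequency and size of second servings or added food eaten, and p_w and W the frequency and size of spills, with sizes as a share of the plated meal. Reported events are taken as fully corrected and unreported ones as uncorrected. Then

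- error in mean recorded intake = −(1 − r)(p_s·S − p_w·W)
- bias in change, with event frequencies constant = (r₂ − r₁)(p_s·S − p_w·W)

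**Assumed inputs.** S = 0.40 and W = 0.10, with p_s from 0.2 to 0.5 and p_w from 0.1 to 0.2. The bracket is then:

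- low: 0.2 × 0.40 − 0.1 × 0.10 = 0.07
- middle: 0.3 × 0.40 − 0.2 × 0.10 = 0.10
- high: 0.5 × 0.40 − 0.2 × 0.10 = 0.18

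**Level, r = 0.5.** Error = −0.5 × 0.07 = −3.5 points, −0.5 × 0.10 = −5.0 points, and −0.5 × 0.18 = −9.0 points of the plated meal.

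**Direction.** The two kinds of event pull in opposite directions. With these sizes the net error is an understatement unless spills are more than 0.40/0.10 = 4 times as frequent as seconds and additions. A meal with only an unreported spill is overstated, by 10 points here.

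**Change from Time 1 to Time 2.**

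- Reporting 0.5 at both times: (0.5 − 0.5) × bracket = 0. The level is wrong but the change is not biased.
- Reporting rises from 0.5 to 0.7: 0.2 × 0.07 = +1.4 to 0.2 × 0.18 = +3.6 points.
- Reporting rises from 0.4 to 0.8: 0.4 × 0.07 = +2.8 to 0.4 × 0.18 = +7.2 points.
- Reporting constant at 0.5, but second servings fall from 0.3 to 0.2 of meals: the true contribution is −0.1 × 0.40 = −4 points and the recorded one is 0.5 × (−4) = −2 points. A real change is halved.

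**Contrast with the delayed controls.** A shift of the same size in both groups cancels when changes are compared. If, for example, reporting rises from 0.5 to 0.7 in the programme group only, the contrast is off by the same +1.4 to +3.6 points.

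**With required prompts.** If every event is captured (r₁ = r₂ = 1), the model's error is 0 in both level and change, apart from error in the amounts parents give.

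**The case against.** The strongest case is that little rests on this measure. The study is a feasibility study, the outcome is exploratory, the Protocol states no efficacy test on photo intake, and a separate child diet questionnaire is given at both times. That stands and sets the priority. It is only partly offset by the Enactment row of the measures table, a primary implementation outcome, which draws on the behavioral outcomes as well as on focus groups and interviews.

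The photo-coding procedure is not shown, and a coder may sometimes see leftovers of an added item in the post-meal photo. This also stands, but it does not help with food eaten completely or with food spilled.

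Three stronger readings are tempting, and the documents do not support them:

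- **Change is biased.** A reader might infer this from the optional field. Equal omission at both times leaves the change unbiased, and a shift alike in both groups cancels in the contrast.
- **Intake is always understated, and differently by group.** Unreported spills push intake upward. The programme activity concerns photos, food groups and portion sizes; it does not mention seconds, spills or additions, and controls meet the same post-meal field at baseline. Better reporting by programme parents at Time 2 is plausible, not shown.
- **One eating occasion must be named.** The text says only that the child's meal is photographed. It does not say that parents may switch occasions, and participant instructions, which are not shown, may settle this. Restricting to one occasion would also narrow the picture of mealtime food quality, so it is a trade-off and not a correction.

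**Conclusion.** The point holds as a weakness in data capture. The corrections that photo-based intake needs are foreseen but optional, so unreported events misstate the level of intake and a blank cannot be read as none. The size cannot be computed from the documents. The illustrative 3.5 to 9.0 points of understatement rests wholly on assumed frequencies, sizes and a reporting rate of one half.

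For the change over time and the contrast with the delayed controls, the finding is a risk and not a demonstrated bias. It needs a shift in reporting or in event frequency, and for the contrast a shift that differs by group. Programme parents' exposure to meal photos and portion sizes before Time 2 makes that possible. Given the exploratory tier, this is a cheap improvement of low priority.

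**What to change.** With each post-meal photo, at both time points and in both groups, require three yes/no answers: second serving taken, food spilled or wasted, item added during the meal. Ask for an approximate amount whenever the answer is yes, and keep the free text optional. A recorded no then differs from a missing answer.

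The cost is a small change to the app form and a few extra taps per meal. Amounts estimated by parents carry some error of their own, so the prompts reduce the misstatement but do not remove it entirely.

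### Does the mailing schedule leave the delayed control group without study balls for the movement-skills assessment?

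*Protocol*

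**What the plan says.** The Intervention Design section lists three programme components, the last being "3) child-centered support materials mailed to participating families". Its Support materials subsection gives these parcels two uses: "Materials to support both assessment (e.g., balls) and programming (e.g., chef's hat and apron, activity dots, scarves, etc.) will be mailed to participants". On number and timing it says only "We anticipate ~3 mailings spread out over the program". The schedule headed "Table 2: Know How Intervention Design" marks support materials at Weeks 0, 3 and 7.

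The Overview places Week 0 inside the intervention: "The intervention will be 10 weeks. Week 0 will be an introduction to the overall study followed by 9 weeks of Know How programming". The Group Discussions subsection counts differently: "During the 9-week intervention, participants will meet via Zoom for 6, 45-60 minute sessions".

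Under Study Design, "Study assessments will be collected at Baseline (Time 1), pre-intervention and at Post-Test (Time 2), post-intervention at the same time for both groups", and "No additional assessments will be collected for the delayed control group at the conclusion of implementation". Child Movement Skills is an exploratory outcome filmed through the app at both times. It comprises 11 skills in four groups, two of which are ball skills.

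**The concern.** The stated purpose of the parcels and their stated timing seem not to fit for the control group. Balls are mailed to support an assessment, yet the only dated mailings belong to the programme calendar. A delayed control group starts its programme after Time 2 and is not assessed again. If the calendar is read as each group's own weeks, every control parcel arrives after both control assessments. The intervention group has received all of its parcels by Time 2.

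Ball skills would then be filmed with study equipment in one group, and with household equipment or none in the other. A between-group difference at Time 2 could partly reflect the ball rather than the child, and no analysis could repair that afterwards.

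A related worry is that Food Photography and Child Movement Skills are collected through the same app that delivers the lessons. The text does not say how controls open the assessments without seeing that content.

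**Working it through.** The protocol gives no figure to reproduce here. The check is a count, followed by a comparison of readings.

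**Mailing weeks.** The support-materials row of the schedule table has 10 columns (Weeks 0 to 9), with marks at Weeks 0, 3 and 7. That is 3 mailings, in line with the anticipated number.

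**Share of the measure that needs a ball.** Locomotor skills: 3 + 3 = 6. Ball skills: 3 + 2 = 5. Total: 6 + 5 = 11. Share: 5/11 = 45%. The other 6/11 = 55% are unaffected.

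**How firm the Week 0 boundary is.** The same table puts group discussions in Weeks 0, 2, 4, 6, 8 and 9, which is 6 sessions. Only 5 of these fall in Weeks 1 to 9. The Group Discussions text nevertheless places all 6 within a 9-week intervention, while the Overview counts 10 weeks including Week 0. The document therefore uses Week 0 loosely, and its position relative to a pre-intervention Time 1 cannot be read off strictly.

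**Which assessments would have study balls.** There are 2 groups x 2 time points = 4 movement assessments. I assume the balls are in the Week 0 parcel; the protocol does not say which parcel holds them.

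| Reading | Intervention, Time 1 | Intervention, Time 2 | Control, Time 1 | Control, Time 2 | Covered |
|---|---|---|---|---|---|
| Each group's own weeks; Time 1 before Week 0 | no | yes | no | no | 1 of 4 |
| Each group's own weeks; Week 0 parcel before Time 1 filming | yes | yes | no | no | 2 of 4 |
| Week 0 study-wide; Time 1 before it | no | yes | no | yes | 2 of 4 |
| Week 0 study-wide; parcel before Time 1 filming | yes | yes | yes | yes | 4 of 4 |
| Balls sent to all participants before Time 1, apart from the programme parcels | yes | yes | yes | yes | 4 of 4 |

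The groups differ at Time 2 only in the first two rows. The first row also leaves the intervention group without balls at Time 1, so nobody would have them at baseline. That sits badly with a sentence saying that balls are mailed to support assessment, and it suggests that the programme calendar was not written to time the assessment kit.

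**The case for a change.** The best case for a change is that the programme calendar is the only supply route described, and that Week 0 also holds the first group discussion and the first app entry. A study-wide Week 0 would therefore need text saying which of its elements controls receive. If Week 0 lies inside the intervention and Time 1 comes before it, even a study-wide parcel misses Time 1. On this argument, no reading equips all four assessments without words the protocol lacks, the remedy is a sentence or two, and unequal equipment cannot be undone later.

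Part of this stands. The visible text does not say when balls reach each group relative to Time 1 and Time 2, and one line would settle it. The step from there to a defect does not stand:

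- The sentence about assessment materials names participants, not one group, and both groups are assessed.
- The number of mailings is approximate and anticipated. An earlier parcel would not breach a fixed schedule.
- The Overview describes Week 0 as introducing the study as a whole, and the document is not consistent on whether it belongs to the intervention.
- The timeline figure by cohort and group would show where each group's Week 0 falls. Its absence from the extracted text is not a gap in the plan.
- The protocol does not say that a study ball is required, so a family using its own ball is not excluded.

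On app access, nothing in the protocol gives controls the lessons early or rules out restricted accounts. App backend data are already collected and record engagement by topic, so any early use of lessons could be checked.

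**Conclusion.** No change to the plan follows. The observation is accurate as far as it goes: mailings are marked at Weeks 0, 3 and 7, assessments are simultaneous, and no separate assessment parcel is described. The conclusion that controls receive no balls before Time 2 holds only if the weeks are each group's own programme weeks and no other parcel is sent. The text fixes neither condition.

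Even if both held, the effect would be confined to 5 of 11 skills in one of five exploratory measures. The primary outcomes of this pilot are feasibility and implementation, and they do not depend on the balls. The locomotor skills and Food Photography do not either.

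What remains is shipping timing and account set-up. A team that has already said it mails balls for assessment will fill these in sensibly when it runs the study.

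### As read, the measures table marks the only listed source for two primary outcomes, Usability and Acceptability, at baseline only; check the marks and, if confirmed, move them to Time 2

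*Protocol*

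**What the plan says.** The measures table in the protocol (Measures, Table 2, Feasibility Pilot Study Measures) lists Usability and Acceptability under Feasibility, labelled as primary. The Usability variables are "Ease of use, complexity, confidence in using, likelihood of use". The Acceptability variables are "Ratings of information helpfulness, goal setting, liking, willingness to recommend, desire for additional information". Each row gives one data source, "2. Experience with Know How Program" (below, the Experience survey). As read, each row has an X under Time 1, nothing under Time 2, and a check mark under IRB Submission.

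The Study Design section fixes what the time columns mean: "Study assessments will be collected at Baseline (Time 1), pre-intervention and at Post-Test (Time 2), post-intervention at the same time for both groups". The table footnote agrees that Time 1 is baseline and Time 2 is after the intervention. For the delayed controls, Study Design adds: "No additional assessments will be collected for the delayed control group at the conclusion of implementation".

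Two other places bear on the point. Under Group Discussions, the questions put to participants include "acceptability of program (Discussion 3"), and the Peer Support row of the measures table likewise names acceptability, timed during the intervention. Under Know-How app, C. Assessments, participants have some contact with the app at baseline: "Two assessments will be built into the app (to complement survey distributed via REDCap) and administered at baseline and post-intervention".

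**The concern.** A survey about people's experience of a programme is marked only at the visit before they receive it. Several of the listed ratings have no meaning at that visit: a parent cannot say whether the information helped, whether they liked the programme, or whether they would recommend it.

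These are primary outcomes of a feasibility study, so they are part of what the pilot exists to deliver. If the survey were fielded as marked, the study would end without the ratings that bear on whether the programme is usable and acceptable. A post-programme survey missed in a short pilot is hard to recover afterwards.

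**Working it through.** No arithmetic applies. The check sets the table rows and the related text side by side.

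**Step 1: the marks as read.** Column order is data source, Time 1, Time 2, IRB Submission.

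| Row | Source | Time 1 | Time 2 | IRB |
|---|---|---|---|---|
| Retention | study records, app data | blank | X | blank |
| Usability | Experience survey | X | blank | check |
| Acceptability | Experience survey | X | blank | check |
| Digital Engagement | app data | blank | X | blank |
| Enactment | behavioural data, focus groups, interviews | X | blank | check |
| Intention to Sustain | focus groups, interviews | X | check | blank |
| Mindful Parenting | survey | X | X | check |

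**Step 2: could a shifted cell explain it?** In Intention to Sustain the check mark lies under Time 2 and the IRB cell is empty. Moving both marks one cell to the right gives X at Time 2 and the check under IRB, so that row has visibly slipped. In Usability and Acceptability the check mark is already under IRB, and the same slip would have moved it. Retention, just above, and Digital Engagement, just below, are read with an X under Time 2 alone, so a Time 2-only mark can survive in this part of the table. A simple one-cell shift is therefore not the explanation. Some other misplacement of the X remains possible.

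**Step 3: what could be answered at Time 1?** The baseline contact with the app consists of two assessments that "will require photo and video upload". That could inform ease of use and complexity in part. Confidence in using the app, likelihood of use and wish for more information could be asked in advance. Helpfulness of the information, liking and willingness to recommend could not. This sorting is a judgement from short labels, since the survey items are not in the protocol.

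**Step 4: is there another source after the programme?** For Usability, none is listed. For Acceptability, the Know How Intervention Design table places Discussions 1 to 6 in Weeks 0, 2, 4, 6, 8 and 9, so Discussion 3 falls in Week 4. The Know Your Self, Know Your Home and Summary modules start in Weeks 5, 7 and 9. The Discussion 3 questions therefore come before those three modules and cannot cover the whole programme.

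**Step 5: could the delayed controls fill the gap?** No. Time 2 falls at the same time in both groups, before the controls receive the programme, and they are not assessed once they have had it.

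**The case against.** The strongest reply is that this is a fault in how the table was read from the PDF and not a fault in the protocol. Intention to Sustain has plainly slipped, and Enactment is broken across two lines. The four rows that carry one X and a check mark and that concern programme experience or results (Usability, Acceptability, Enactment, Intention to Sustain) all read as Time 1. Retention and Digital Engagement, with one X and no check mark, read sensibly as Time 2. The timing entries for the Screener (before enrolment) and Peer Support (during the intervention) also land under Time 1, with the check mark still under IRB, although neither means the baseline visit. Content under Time 1 is thus not sure proof of the printed column. This stands: a reading fault cannot be excluded, and Step 2 rules out only the simplest form of it.

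Three further replies also stand. The study timeline figure is not shown, so a reader who infers that this table is the only place where the survey is scheduled goes too far. Nothing says that the REDCap events are set up from this table, so a mis-fielded survey cannot be presented as the expected result. The title of the survey would also probably alert study staff.

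These replies do not remove the conflict on the page. Both rows, as read, place a programme-experience survey before the programme, and no text shown says otherwise.

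**Conclusion.** The point holds as a conditional correction, with low to medium confidence. As read, the table marks the sole listed source for Usability and Acceptability at baseline and not after the programme, which conflicts with what the survey asks. On that reading, Usability has no listed post-programme measure, and Acceptability has only mid-programme questions in Week 4.

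This rests on two assumptions: that the marks as read match the printed table, and that the figure not shown does not schedule the survey at Time 2.

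A reader might infer more, but the documents do not support it:

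- That the study will certainly lack usability and acceptability data. The marks are unconfirmed and may be a slip that staff would catch.
- That nothing in the survey could be answered at baseline. Some of the variables could be, and baseline app contact informs others in part.
- That Enactment and Intention to Sustain are also wrongly scheduled. The second row is visibly shifted. The first draws partly on behavioural measures taken at both times. Neither shows an error in the plan.

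**What to change.** First, check the marks in all four rows (Usability, Acceptability, Enactment, Intention to Sustain) against the original table. If the Usability and Acceptability marks are under Time 2 there, nothing needs to change in those two rows.

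If they do stand under Time 1, move both to Time 2. State that the Time 2 Experience survey is analysed in the immediate-intervention group, because the delayed controls have not had the programme by then and are not assessed later.

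The cost is two marks in the schedule and one sentence on who is analysed, with no added visits or instruments.
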